IMIDs and proteasome inhibitors have been used post salvage ASCT as maintenance treatment, however cytopenias, toxicities, and resistance due to previous exposure to these drugs, decrease their applicability. The newly FDA approved monoclonal antibody daratumumab has established efficacy as a single agent in relapsed and refractory disease, however is not FDA approved as a maintenance option post autologous stem cell transplant. It is an IgG1 kappa human monoclonal antibody directed against CD38. It induces apoptosis directly through Fc mediated cross linking and immune mediated tumor lysis through complement dependent cytotoxicity, antibody dependent cell mediated cytotoxicity and antibody dependent cellular phagocytosis. Thus its potential role as maintenance therapy post salvage transplant is promising and worthy of investigation.

Daratumumab was approved by the FDA in November 2015 for IV infusion. More recently, in May 2020, FDA approved its subcutaneous formulation, daratumumab/hyaluronidase-fihj. Its advantages include a fixed-dose formulation, short administration time of 3-5 minutes, which is significantly shorter than the currently used IV formulation that is given over hours, and a significant reduction in infusion-related reactions. In the Phase 3 COLUMBA study (19) supporting the approval, daratumumab and hyaluronidase-fihj demonstrated a consistent overall response rate (ORR) and pharmacokinetics and a similar safety profile compared with intravenous daratumumab in patients with relapsed or refractory multiple myeloma. In addition, there was a nearly two-thirds reduction in systemic infusion-related reactions with daratumumab and hyaluronidase-fihj compared to intravenous daratumumab (13 percent vs. 34 percent, respectively).

Pomalidomide is the third-generation immunomodulatory drug (IMiD) that has been approved by the FDA in June 2017 for use in relapsed/refractory multiple myeloma in combination with daratumumab IV based on the results of

EQUULUS trial (20). As most of the myeloma patients eligible for salvage ASCT have been exposed to daratumumab, and are refractory to the 2nd generation IMiD, lenalidomide, we hypothesize that a combination of daratumumab and hyaluronidase-fihj plus pomalidomide will improve the patient accrual, and the disease control.

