3.1.6 Blood Typing and Cross-matching Interference

Red cell and platelet transfusions will be required for some patients undergoing maintenance therapy post autologous stem cell transplantation. It has previously been reported that daratumumab binds to CD38 expressed on the surface of red blood cells. Although this additional activity may interfere with blood typing and cross-matching, no AEs related to hemolysis have been reported. In previous trials, patients had their blood types assessed before their first daratumumab infusion. They were also encouraged to carry a card indicating their blood type for the duration of the study. In the event of a positive Coombs

test, individual blood banks used a variety of mitigation methods to safely provide blood products. Blood banks were also made aware that this effect could persist for up to 6 months after cessation of daratumumab treatment.

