4.2 Exclusion Criteria

Patients meeting any of the following exclusion criteria are not to be enrolled in the study:

1. Major surgery within 14 days before the first dose of study drug.
2. Radiotherapy within 14 days before enrollment.
3. Non-secretory disease, plasma cell leukemia, or previous allogeneic transplant.
4. Known active central nervous system involvement.
5. Inability or unwillingness to comply with the drug administration requirements.
6. Female subject is pregnant or lactating.
7. Seropositive for human immunodeficiency virus (HIV).
8. Seropositive for hepatitis B (defined by a positive test for hepatitis B surface antigen [HBsAg]). Subjects with resolved infection (ie, subjects who are HBsAg negative but positive for antibodies to hepatitis B core antigen [anti-HBc] and/or antibodies to hepatitis B surface antigen [anti-HBs]) must be screened using real-time polymerase chain reaction (PCR) measurement of hepatitis B virus (HBV) DNA levels. Those who are PCR positive will be excluded. EXCEPTION: Subjects with serologic findings suggestive of HBV vaccination (anti-HBs positivity as the only serologic marker) AND a known history of prior HBV vaccination, do not need to be tested for HBV DNA by PCR.
9. Seropositive for hepatitis C (except in the setting of a sustained virologic response [SVR], defined as aviremia at least 12 weeks after completion of antiviral therapy).

10. Patients with a known history of asthma or chronic obstructive pulmonary disease with a forced expiratory volume in 1 second (FEV1) <50% of predicted normal.
11. Patients with moderate or severe persistent asthma within the past 2 years and currently uncontrolled asthma of any classification.
12. Infection requiring IV systemic antibiotic therapy within 7 days before C1D1 of therapy.
13. Known allergy to any of the study medications, their analogues, or excipients in the various formulations.
14. Failure to have fully recovered (i.e., <= grade 2 toxicity) from the effects of prior chemotherapy regardless of the interval since last treatment.
15. Patient is refractory or resistant to daratumumab and pomalidomide.
16. Co-morbid systemic illnesses or other severe concurrent disease that, in the judgment of the investigator, would make the patient inappropriate for entry into this study or interfere significantly with the proper assessment of safety and toxicity of the prescribed regimens.
17. If patient was unable to tolerate daratumumab or pomalidomide in the past.

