5.0 Treatment Plan

5.1 Overall Design and Plan of Study

This will be a single arm, open label phase II, single center study of maintenance therapy with daratumumab/hyaluronidase-fihj and pomalidomide post salvage ASCT in patients with multiple myeloma.

The total number of patients to be treated in this study is 56 evaluable patients.

Patients should complete 2 cycles of therapy to be evaluable. For patients who receive fewer than 2 cycles due to progressive disease will be considered evaluable. Patient who received < 2 cycles due to AEs will be inevaluable for efficacy (response). All the other analysis will be conducted using intention to treat dataset.

Patients will have standard restaging studies prior to initiation of therapy. Standard post transplant therapy per institutional guidelines will be unaltered including prophylactic antibiotics, vaccinations and restaging.

Each cycle will be defined as a 28 day cycle. Drug holidays and break in therapy including those due to holidays, physician discretion and drug delivery are allowed as needed.

5.2 Daratumumab 1800 mg/hyaluronidase-fihj 30,000 units will be given SC weekly for weeks 1-8, followed by every 2 weeks for weeks 9-24, and then every month for weeks 25 until progression. On day 1 of each cycle, doses may be held if clinically indicated (i.e., active infections) for up to 4 weeks. If longer than 4 weeks, the PI will

evaluate and determine if the patient can continue on trial or must be taken off study. After day 1 of each cycle, subsequent doses may be held/skipped if clinically indicated (i.e., active infections) per PI or treating physician's discretion.

If daratumumab administration does not commence within the specified window (Appendix A), then the dose will be considered a missed dose. Administration may resume at the next planned dosing date. A missed dose will not be made up. Any adverse event deemed to be related to daratumumab that requires a dose hold of more than 28 days will result in permanent discontinuation of daratumumab. Subjects who miss ≥ 3 consecutive planned doses of daratumumab for reasons other than toxicity will be withdrawn from treatment, unless, upon consultation with the sponsor and review of safety and efficacy, continuation is agreed upon.

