7.2 Futility and Toxicity Monitoring

The secondary endpoint is the complete remission rate (CRR). Remission will be evaluated 6 months after daratumumab and hyaluronidase-fihj plus pomalidomide maintenance therapy (approximately 9 months post ASCT). Complete remission is defined as achieving a negative immunofixation of serum and urine, disappearance of any soft tissue plasmacytomas, and < 5% plasma cells in bone marrow. In patients for whom only measurable disease is by serum FLC level, normal FLC ratio of 0.26 to 1.65 in addition to CR criteria is required. The futility and toxicity will be monitored during the study.

We desire that the CRR is at least 10% and the dose-limiting toxicity rate is no higher than 33%. Toxicity is defined as treatment-related unmanageable toxicities, including grade 3 non-hematologic effects or grade 4 hematologic effects, that require delay or termination of the treatment during cycle one. Futility and toxicity will be monitored by the Bayesian stopping boundaries calculated on the basis of beta-binomial distributions using the method of Thall, Simon, and Estey (30). Independence is assumed between CR and toxicity. Patients will be monitored in cohorts of size (8).

We will enroll a minimum of 16 patients before stopping. The following stopping rules and boundaries were developed using the Multc Lean application (version

2.1) from the MDACC Biostatistics department. The stopping rules are as follows:

$$\Pr [\theta_E < 0.10 | \text{data}] > 0.90$$

$$\Pr [T_E > 0.33 | \text{data}] > 0.95$$

Enrollment will be stopped early if there is > 90% probability that the CRR is < 10% or there is > 95% probability that the toxicity rate is higher than 33%. The notation θ_E denotes the marginal remission rate, assuming that θ_E follows a prior distribution of beta (0.2, 1.8). T_E denotes the toxicity rate, assuming that T_E has a prior distribution of beta (0.66, 1.34). The corresponding stopping boundaries for futility monitoring are as follows: enrollment will be stopped early due to futility if (# of patients with remission) / (# patients evaluated) \leq 0/16-24, 1/32, 2/40-48, or 3/56.

Stopping boundaries corresponding to this probability criterion for toxicity will terminate the trial if (# of patients with toxicity) / (# patients evaluated) \geq 9/16, 13/24, 16/32, 19/40, 22/48, or 25/56.

We will suspend accrual while waiting to assess patient outcomes.

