Study Day:	-28 to -1	1 (+/- 3 days)	8 (+/- 3 days)	15 (+/- 3 days)	22 (+/- 3 days)	1 (+/- 3 days)	15 (+/- 3 days)	1 (+/- 7 days)	Post-Treatment 7 days (+/- 7 days)	Post-Treatment 90 (+3) days q12wks (+/- 7 days)		
Disease Evaluations (Blood/Urine) ^e	-14 to -1	Cycles 1 & 2			Cycles 3-6		Cycles 7+	EOT ^a	FUP ^b	Survival ^{b,i}		
Serum beta 2-microglobulin	X											
QIg (IgA, IgM, IgG, IgD, IgE) ⁿ	X	Every 2-3 cycles during treatment (+/- 7 days)										
SPEP	X						X	X ^b				
UPEP (24-hr urine sample)	X						X	X ^b				
Serum calcium corrected for albumin	X						X	X ^b				
Serum FLC & serum/urine immunofixation	X						X	X				
Disease Evaluations (Other)	-42 to -1											
Bone marrow aspirate/biopsy and assessment of MRD	X	To confirm CR (including sCR) ^j Bone marrow biopsy examination with NGF-based MRD testing at 6 months from the start of maintenance (+/- 2 weeks) then as clinically indicated										
Skeletal survey	As clinically indicated	As clinically indicated										

Assessments	Screening Phase	Study Visits								Follow-up Phase									
		Treatment Phase (28-day cycles)							EOT ^a	FUP ^b	Survival ^{b,i}								
		Cycles 1 & 2			Cycles 3-6		Cycles 7+												
Study Day:	-28 to -1	1 (+/- 3 days)	8 (+/- 3 days)	15 (+/- 3 days)	22 (+/- 3 days)	1 (+/- 3 days)	15 (+/- 3 days)	1 (+/- 7 days)	Post-Treatment 7 days (+/- 7 days)	Post-Treatment 90 (+3) days	q12wks (+/- 7 days)								
Assess extramedullary plasmacytomas	X ^k	Measurable sites every 4 weeks (if applicable) (for physical examination) and every 12 weeks (for radiologic examination) for subjects with a history of plasmacytomas or as clinically indicated for others								X ^l									
Abbreviations: COPD=chronic obstructive pulmonary disease; CR=complete response; CT=computed tomography; ECOG=Eastern Cooperative Oncology Group; EORTC=European Organization for Research and Treatment of Cancer; EOT=End-of-Treatment; FFPE= formalin-fixed paraffin embedded; FLC=free light chain; FUP=Follow-up Phase; ICF=informed consent form; IV=intravenous; Ig=quantitative immunoglobulins; MRD=minimal residual disease; MRI=magnetic resonance imaging; PBMCs=peripheral blood mononuclear cells; PK=pharmacokinetics; PD=progressive disease; PFS=progression-free survival; SAE=serious adverse event; sCR=stringent CR; SPEP=Serum M- protein quantitation by electrophoresis; UPEP=urine M-protein quantitation by electrophoresis																			

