Note: Study drug is defined as daratumumab and pomalidomide.																			
a) To occur within 7 days after discontinuation of all study treatment.																			
b) In the 90 (+3) days after the last dose of daratumumab for safety follow-up visits. For subjects who discontinue study treatment before PD, disease evaluations should continue to be performed at the frequency specified below until confirmed PD, death, start of a new anticancer treatment, withdrawal of consent to study participation, or end of the study, whichever occurs first. Once PD is confirmed, subsequent disease evaluation time points are not required.																			
- Every 8-12 weeks (± 3 days), at clinician's discretion: SPEP and 24-hour UPEP assessments, and serum calcium corrected for albumin																			
- Every 4 weeks (± 3 days), or at clinician's discretion: physical examination of extramedullary plasmacytomas if applicable																			
- Every 12 weeks (± 14 days), or at clinician's discretion: radiologic imaging of extramedullary plasmacytomas if applicable																			
- When CR is suspected or maintained: serum FLC, serum and urine immunofixation																			
- As clinically indicated: skeletal survey																			

- Evidence of clinical relapse will also be documented at the time at which it is first detected.

After PD is determined, patient will be taken off study and no further study evaluations will be needed.

- c) Blood pressure is to be measured at the following time points on Cycle 1 Days 1: immediately pre-administration, at the end of administration, 30 minutes post administration, 60 minutes post administration, and then hourly until 6 hours post administration. On Cycle 1 Day 8: immediately pre-administration, at the end of administration, 30 minutes post administration, 60 minutes post administration, and 120 minutes post administration. On Cycle 1 Day 15 onward: immediately pre-administration, at the end of administration, 15 minutes post administration. Infusion observation times and vital signs may be adjusted per PI discretion.
- d) Pre-infusion medications to be given before all daratumumab infusions (if necessary, oral pre-infusion medications may be administered at the subject's home on the day of the infusion, provided they are given within 3 hours prior to the infusion)
- e) Unless otherwise stated, all blood and urine samples must be obtained before administration of study treatment.

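### Section 7.2 has no rule for a daratumumab band on serum immunofixation, so a true CR can be scored as non-CR and the CRR can only be biased downward by it

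*Combined protocol and SAP*

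**What the plan says.** - **CR definition (section 7.2).** "Complete remission is defined as achieving a negative immunofixation of serum and urine", together with disappearance of soft tissue plasmacytomas and fewer than 5% marrow plasma cells. Nothing is said about a band that comes from treatment.
- **Drug type (section 2.1).** "It is an IgG1 kappa human monoclonal antibody directed against CD38".
- **Timing of the reading (section 7.2).** "Remission will be evaluated 6 months after daratumumab and hyaluronidase-fihj plus pomalidomide maintenance therapy (approximately 9 months post ASCT").
- **Dosing at that time (section 5.2).** After the weekly phase, dosing is "followed by every 2 weeks for weeks 9-24, and then every month for weeks 25 until progression". Table 1 in section 3.1.2 gives 8 weekly and 8 two-weekly doses, with the four-weekly phase starting at week 25.
- **Assays (Appendix A).** The schedule lists SPEP, 24-hour UPEP and "Serum FLC & serum/urine immunofixation". For patients who stop treatment before progression, footnote b adds: "When CR is suspected or maintained: serum FLC, serum and urine immunofixation". No antibody-specific test is listed. Footnote e has samples drawn before dosing.
- **Interference that is addressed (section 3.1.6).** Only transfusion testing: "this additional activity may interfere with blood typing and cross-matching".
- **Population (section 4.2).** The disease-type exclusion reads "Non-secretory disease, plasma cell leukemia, or previous allogeneic transplant". IgG-kappa myeloma is therefore eligible.
- **Role of CRR.** Section 1.1 makes it the primary objective. Section 7.2 calls it secondary but uses it for the futility rule, and section 7.3 reports it with a 95% credible interval.

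**The concern.** Immunofixation identifies a monoclonal protein by its heavy and light chain. A circulating monoclonal IgG kappa is therefore the kind of protein that the test is built to show, whether it comes from the tumour or from a syringe. The endpoint assay is read while such an antibody is being given, and the definition does not separate the two sources.

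The error runs one way. A drug band can make a negative result positive, but it cannot hide a disease band and so create a CR. Enrolling more patients does not remove a bias of this kind. It would carry through to the CRR, to its credible interval and to the remission count that decides whether enrolment stops for futility. The operating-characteristics table in section 7.2 is indexed by the true response probability, so it takes the scored CR rate to be the true one.

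**Working it through.** **1. Is the drug present when CR is read?** Two-weekly doses from week 9 fall at weeks 9, 11, ..., 23, and the first four-weekly dose is at week 25. Six months is about week 26, and the marrow window is ±2 weeks. With doses given as planned, a pre-dose sample at week 25 is about two weeks after the last injection, and one before the week 29 dose is about four weeks after. The reading is on treatment. The documents give no serum level and no assay detection limit.

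**2. Reproduce the plan's own figures.** With the Beta(0.2, 1.8) prior, the posterior after x remissions in n patients is Beta(0.2 + x, 1.8 + n − x). Enrolment stops if Pr(CRR < 0.10) > 0.90.

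| n | largest x that stops | Pr at x | Pr at x + 1 |
|---|---|---|---|
| 16 | 0 | 0.984 | 0.777 |
| 24 | 0 | 0.995 | 0.898 |
| 32 | 1 | 0.954 | 0.821 |
| 40 | 2 | 0.905 | 0.756 |
| 48 | 2 | 0.951 | 0.856 |
| 56 | 3 | 0.918 | 0.808 |

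These are the stated boundaries. An exact binomial recursion over the looks at 16, 24, 32, 40 and 48, with CR and toxicity independent, also returns the table in 7.2:

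- CRR 10%, toxicity 15%: 0.315 and 46.0 patients (stated 0.32 and 46.0).
- CRR 25%, toxicity 20%: 0.013 and 55.5 (stated 0.013 and 55.5).
- CRR 30%, toxicity 20%: 0.005 and 55.8 (stated 0.005 and 55.8).

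The plan's arithmetic is sound. The question is what goes into x.

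**3. Effect of misreading.** Let p be the true CRR, s the share of true CRs with IgG-kappa disease, and m the share of those scored non-CR because of a drug band. Then:

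scored CRR = p × (1 − s × m)

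Neither s nor m is in the documents. Assumed ranges are s = 0.25 to 0.45 and m = 0.5 to 1.0.

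- Mildest corner: 1 − 0.25 × 0.5 = 0.875.
- Most severe corner: 1 − 0.45 × 1.0 = 0.55.

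The scored rate then goes through the recursion of step 2, with the futility boundary only:

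| True CRR | Scored CRR | Early stop, no misreading | Early stop, with misreading |
|---|---|---|---|
| 20% | 11.0-17.5% | 0.034 | 0.061-0.257 |
| 28% | 15.4-24.5% | 0.006 | 0.012-0.098 |
| 40% | 22.0-35.0% | 0.0003 | 0.001-0.022 |

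A wider range, s = 20-50% and m = 25-100%, gives factors from 1 − 0.5 × 1.0 = 0.50 to 1 − 0.2 × 0.25 = 0.95. A true 28% is then scored as 14.0-26.6%, with early stopping of 0.008-0.134. If every drug band is resolved (m = 0), the scored CRR is the true CRR and the table in 7.2 stands.

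**The case against.** **The documents do not say that daratumumab shows on immunofixation.** This is correct. It is inferred from the stated antibody class, from what the test detects and from ongoing dosing. The inference supports a possible error with a known direction. It does not support a claim about how often the error occurs.

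**The reader would cope.** Taken fully literally, a drug band would make the test positive in every isotype, and nobody would read an IgA-lambda patient that way. SPEP and immunofixation are scheduled at screening, so a comparison exists. Section 1.1 refers to IMWG criteria, and section 9.1 gives the Principal Investigator the last word on response where opinions differ. These points may well reduce the error, and they are why it falls chiefly on IgG-kappa disease. None of them is a rule, however. Section 7.2 writes out its own definition, and unwritten case-by-case calls in an open-label single-arm trial are a poor substitute for one.

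**Some CRs may precede the drug.** Section 1.1 counts CR within 9 months of transplant, so a CR recorded before the first study dose might count without study-drug interference. Section 7.2 places the evaluation at 6 months of maintenance, which leaves this unclear. If such CRs count, the effect is smaller.

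**Tempting stronger readings.** A reader might infer that false futility stopping is the main danger. At a true CRR of 28% or 40% that risk stays below 0.10 even in the worst assumed corner. The 0.257 at a true CRR of 20% needs 45% IgG-kappa disease and every such CR misread. A reader might also infer a biased comparison with the 28% CR rate in section 2.1. That rate is background: the futility threshold is 10%, and section 7.3 plans an estimate with a credible interval, not a test against 28%.

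**Conclusion.** The point stands as a gap in the endpoint definition. CR depends on a negative serum immunofixation, read during treatment with an IgG1 kappa antibody, and the plan does not say how to score a band caused by that antibody. By this route the bias in CRR, its credible interval and the futility count can only be downward.

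The size is unknown. The figures in the working are a sensitivity range resting on an assumed isotype share and misreading rate, and they should not be quoted as the expected loss. At plausible CR rates the more important consequence is a CRR estimate that is too low, rather than a false stop. The correction is worth making before CR is scored, because it costs little and uses samples that are already scheduled.

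**What to change.** 1. **Band rule in section 7.2.** In a patient who meets all other CR criteria, an IgG-kappa band attributable to daratumumab and distinct from the screening M-protein does not by itself exclude CR. Screening follows the transplant, so where no M-protein remained at screening, compare with the last recorded disease band.
2. **Bands that cannot be separated.** Use a daratumumab-specific reflex immunofixation on the same serum, if the laboratory already offers it. Add a line to Appendix A.
3. **Still unresolved.** Flag the patient, and keep the patient in the denominator as non-CR for the main CRR estimate and for the futility count. The looks then stay at 16, 24, 32, 40, 48 and 56 patients, and the stated boundaries still apply.
4. **Reporting in section 7.3.** Add a sensitivity CRR that counts unresolved patients as CR. Show it beside the 6-month marrow and MRD result that is already scheduled, and give CRR for IgG-kappa and other isotypes separately.

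**Cost.** Wording in 7.2, 7.3 and Appendix A, and possibly a reflex test on existing serum in a few patients. No visit or biopsy is added. Some conservative bias remains from unresolved cases, but the sensitivity CRR bounds it.

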1.0 Objectives

1.1 Primary Objective

To estimate the complete remission rate (CRR) by the International Myeloma Working Group (IMWG) criteria within 9 months post salvage auto-transplant with subcutaneous daratumumab and hyaluronidase-fihj plus pomalidomide maintenance therapy starting approximately 3 months post salvage auto-transplant in patients with relapsed myeloma.

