2.0 Background

2.1 Overview of Disease/Maintenance Therapy post salvage ASCT

Treatment for multiple myeloma has changed significantly over the past decade. Induction therapy followed by upfront autologous stem cell transplant (ASCT) with melphalan 200 mg/m² has shown significantly improved progression free survival and quality of life for patients with newly diagnosed multiple myeloma (MM).

Maintenance Therapy:

Furthermore, multiple randomized phase III trials have demonstrated significantly improved PFS and OS with the use of continued lenalidomide maintenance therapy post initial ASCT. However, despite these substantial improvements in therapy, the majority of patients will relapse 3-4 years later (1-7).

Salvage ASCT:

Due to earlier diagnoses and improved therapies, MM patients are living significantly longer and many are eligible for second ASCT that can yield a meaningful duration of remission. On the other hand, other patients may not

undergo ASCT in first remission, either due to aggressive disease which may relapse during 1st line induction therapy (including an IMID) or due to preference. Multiple studies have been conducted evaluating salvage ASCT and all demonstrated chemosensitivity and duration of remission after first ASCT were the most important prognostic factors for subsequent long-term disease control (8-17). For patients undergoing salvage ASCT, either as a second transplant or as a first transplant with previous relapse to induction therapy, no standard maintenance therapy has been established post transplant. In a recent study evaluating the addition of lenalidomide to melphalan conditioning for salvage transplant, complete remission rates in both groups (first ASCT after relapsed disease or second ASCT) is similar at 28%, with time for best response of 16-732 days (18).

Maintenance with Daratumumab and Pomalidomide post salvage ASCT:

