4.0 Patient Eligibility

4.1 Inclusion Criteria

Each patient must meet all the following inclusion criteria to be enrolled in the study:

1. Patient must have had relapsed disease prior to transplant, or undergone previous ASCT, followed by relapse and at least a partial response to salvage therapy.
2. Eligible patients will be enrolled in the protocol no less than 60 days and must be initiated no longer than 180 (+/- 14) days post ASCT.
3. Male or female patients 18 years or older.

4. Patients must have an Eastern Cooperative Oncology Group (ECOG) status of 0 to 2.
5. Patients' clinical laboratory values and toxicity must be as specified below within 14 days before the first dose of the study drug:
 - Platelet count $\geq 50,000/\text{mm}^3$
 - Absolute neutrophil count $\geq 1000/\text{mm}^3$ (no growth factors within 5 days)
 - Alanine aminotransferase (ALT) and aspartate aminotransferase (AST) $\leq 3 \times \text{ULN}$
 - Creatinine $\leq 2.5 \text{ mg/dL}$
 - Recovered (i.e., \leq grade 2 toxicity) from the reversible effects of autologous stem cell transplant.
6. Voluntary written informed consent before performance of any study-related procedure not part of normal medical care must be obtained, with the understanding that consent may be withdrawn by the subject at any time without any prejudice to future medical care.
7. Left ventricular ejection fraction $\geq 40\%$ (at the patient's last recorded echocardiogram (this could refer to pretransplant ECHO. ECHO may be repeated if the PI considers a repeat ECHO) No uncontrolled arrhythmias.

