The associations between/among safety data, prognostic factors, and the response will be assessed using student t-test/Wilcoxon rank test, ANOVA/Kruskal-Wallis test, chi-squared test/Fisher's exact test, or Logistic regression model as appropriate. Complete remission rate will be estimated along with a 95% credible interval.

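### The pooled CRR appears to count patients already in CR when maintenance starts, so it cannot show what maintenance adds, and the 10% futility floor gives little protection against a regimen that converts nobody

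*Combined protocol and SAP*

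**What the plan says.** Section 1.1 opens the CRR window at transplant, not at the first maintenance dose: CR is counted "within 9 months post salvage auto-transplant with subcutaneous daratumumab and hyaluronidase-fihj plus pomalidomide maintenance therapy starting approximately 3 months post salvage auto-transplant". Section 7.2 places the assessment at one time: "Remission will be evaluated 6 months after daratumumab and hyaluronidase-fihj plus pomalidomide maintenance therapy (approximately 9 months post ASCT"). It describes a state: "Complete remission is defined as achieving a negative immunofixation of serum and urine, disappearance of any soft tissue plasmacytomas, and < 5% plasma cells in" (the last item refers to the marrow). A normal free light chain ratio is added where that is the only measurable disease.

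On disease status, the first inclusion criterion in section 4.1 reads "Patient must have had relapsed disease prior to transplant, or undergone previous ASCT, followed by relapse and at least a partial response to salvage therapy". Nothing in 4.1 or 4.2 excludes a patient already in CR after the salvage transplant. Enrolment opens 60 days after transplant.

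Section 7.2 sets the efficacy floor and the toxicity ceiling together, both in percent: "We desire that the CRR is at least 10% and the dose-limiting toxicity rate is no higher than 33". The futility rule stops enrolment if the posterior probability that CRR is below 10% exceeds 0.90, under a beta(0.2, 1.8) prior. No reason is given for 10%. Section 2.1 describes a study of lenalidomide added to melphalan conditioning for salvage transplant, in which "complete remission rates in both groups (first ASCT after relapsed disease or second ASCT) is similar at 28%, with time for best response of 16-732" (the range is in days).

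For the analysis, section 7.3 says only: "Complete remission rate will be estimated along with a 95% credible interval". It names no reference rate and no split by CR status at the start of maintenance. That status is available: section 5.1 calls for restaging before therapy, and Appendix A schedules serum FLC and immunofixation at days -14 to -1 and marrow with MRD at days -42 to -1.

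**The concern.** A patient who reaches CR from the transplant and simply remains there appears to count as a responder. The same pooled rate can then arise from quite different situations: a regimen that moves many patients into CR, or a cohort that entered with many CRs and gained none. The planned estimate and interval cannot tell these apart.

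The monitoring rule has the same weakness. It is the plan's only stopping rule for efficacy, and its floor of 10% could be met by transplant responses alone. The trial could accrue in full, and report a CRR well above its stated floor, without any patient having converted on maintenance.

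**Working it through.** **1. Reproduce the plan's boundaries.** Inputs from 7.2: prior beta(0.2, 1.8), reference 0.10, cut 0.90, looks every 8 patients from 16. With x CRs among n patients, stop if P(θ < 0.10) > 0.90, where θ has a beta(0.2 + x, 1.8 + n − x) distribution. The posterior probabilities on either side of each boundary are:

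| n | largest x that stops | P(θ < 0.10) at that x | at x + 1 |
|---|---|---|---|
| 16 | 0 | 0.984 | 0.777 |
| 24 | 0 | 0.995 | 0.898 |
| 32 | 1 | 0.954 | 0.821 |
| 40 | 2 | 0.905 | 0.756 |
| 48 | 2 | 0.951 | 0.856 |
| 56 | 3 | 0.918 | 0.808 |

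These are the six boundaries printed in 7.2.

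**2. Reproduce the operating characteristics.** An exact binomial recursion through the looks, with CR and toxicity independent and the look at 56 not counted as early, gives a stop probability of 0.315 at CRR 10% and toxicity 15% (table: 0.32). It gives 0.0051 at 30% and 20% (table: 0.005). All 15 rows agree within 0.006. The arithmetic of the rule is sound.

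**3. Apply the rule to a regimen that converts nobody.** Let q be the share in CR at the start of maintenance, r the share of these still in CR at month 6, and c the conversion rate among the rest. Then CRR = q·r + (1 − q)·c. With r = 1 and c = 0, CRR = q. The documents do not give q, so a range is assumed. Futility looks only:

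| q (assumed) | true CRR | P(futility stop before patient 56) |
|---|---|---|
| 10% | 10% | 0.315 |
| 15% | 15% | 0.107 |
| 20% | 20% | 0.034 |
| 28% | 28% | 0.0055 |

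Most of each figure comes from the first look, where stopping requires no CR in 16: 0.90^16 = 0.185 at q = 10%, and 0.72^16 = 0.0052 at q = 28%.

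**4. What the final report could look like.** Take q = 28% as an illustration: 0.28 × 56 ≈ 16 patients in CR at entry and 40 not. If all 16 hold CR and none of the 40 converts, the pooled CRR is 16/56 = 28.6%, with a 95% credible interval of 17% to 40% under the plan's prior. In the same data the conversion rate is 0/40. Its posterior is beta(0.2, 41.8), with a 97.5% quantile of 3.6%. The pooled figure conceals this.

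**The case against.** The strongest reply is that the rule does what it claims. A futility floor is not an efficacy test, the aim in 1.1 is to estimate, and the table in 7.2 openly shows low stopping probabilities at CRRs of 20% to 40%. That stands: nothing is miscalculated or hidden, and the height of a floor is a design choice. It does not remove the need to say what the floor leaves uncovered, or why it is 10% when the background cites 28%.

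A reader might infer that 28% is the transplant-only CR rate, so that an inactive regimen would certainly finish near 28%. The documents do not support this. The figure comes from lenalidomide plus melphalan conditioning, with best response as late as 732 days. They do not say whether those patients had maintenance, how many were in CR at 60 to 180 days, or how many had lost CR by month 9.

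A reader might also infer that only conversions speak to maintenance, and that futility should count conversions alone. That goes too far. Late deepening of the transplant response also produces conversions, and keeping patients in CR may itself be an effect of maintenance. The same boundaries applied to non-CR patients at 16, 24 and 32 would stop with probability 0.60 at a 5% conversion rate. If 28% enter in CR, the look at 40 non-CR patients falls at 40/0.72 ≈ 56 enrolled, which is full accrual.

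The verb in the CR definition could mean newly reached CR. Against that, the window in 1.1 opens at transplant, and neither the denominator in 7.2 nor the evaluability rule in 5.1 removes patients already in CR. If new CR is meant, the plan must say so.

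Lastly, 7.3 plans to relate prognostic factors to response, and CR at entry could be one of them. It is not named.

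**Conclusion.** The concern holds in a limited form. As written, CRR appears to include CR already present when maintenance starts; this is inferred from the absence of any exclusion or conversion requirement, since no sentence states it. On that reading the pooled CRR cannot separate CR at entry from CR gained on maintenance.

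The 10% floor then gives little protection against a regimen that converts nobody: the stop probability falls from 31.5% to 10.7%, 3.4% and 0.55% as the entry share rises from 10% to 15%, 20% and 28%. These figures assume that every patient in CR at entry stays in CR; losses would lower the CRR and raise the chance of stopping. The entry shares are assumptions, but the conclusion does not depend on 28%, because protection is already weak at 15% to 20%.

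This is a matter of endpoint definition and reporting. It is not an error in the boundaries, and it does not establish that the regimen would look better than it is.

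**What to change.** In 7.2:
- State whether CRR includes patients already in CR at the start of maintenance.
- State that the 10% rule is a floor and does not protect against a regimen that adds nothing to the transplant CR rate.
- Give the reason for 10% in light of the 28% cited in 2.1.

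In 7.3, tabulate CR status at the pre-maintenance restaging and report, each with a 95% credible interval:
- overall CRR;
- conversion to CR among patients not in CR at start;
- CR maintained among those in CR at start.

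Add that, without a control arm, conversions may partly reflect late deepening of the transplant response.

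The cost is protocol and SAP wording plus one table, with no new visits or tests. If the 10% floor is kept, the boundaries and the operating-characteristics table stand unchanged. The drawback is precision: the conversion estimate rests on fewer patients, about 40 of 56 if 28% enter in CR, so its interval will be wider than one based on all 56.
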